### ***Assessments.***

The complete assessment battery will be performed at the pre-intervention assessment (*Baseline Assessment*, V1) visit, at *Mid-Intervention* assessment (V3) visit and at the post-intervention assessment (*End of Study*, V4) visit. For a full list of all assessments and administration times, please direct your attention to the *Description of Assessments* or *Appendix I*. We will use assessments of functional abilities to determine the degree of transfer of benefit to real-world experience (e.g., symptoms, social functioning, quality of life).

All assessments will be administered to all participants; alternate forms of the assessments will be used when available to mitigate test-retest effects. Performance on all measures will be scored, submitted into the study database, and monitored for accuracy and integrity. Any discrepancies in scoring will be resolved by referring to the raw data collected during the assessment visit(s).

## **Description of Assessments**

### ***Clinical and Neuropsychological assessments and characterization***

The study will employ empirically validated assessment measures specific to ASD.

Collectively, we have chosen a battery based on five key criteria (when possible), including 1) existing standardization, to ensure reliable data collection procedures, 2) sensitivity to the impairment typical of this study population, 3) normative data availability, 4) reasonable test-retest stability (i.e., to control for potential participant improvement through strategy learning over repeated measures) for use in a treatment trial with two repeated measures, and 5) good

sensitivity to change following remediation. Several measures will be used to provide gross clinical characterization.

### ***Cognitive Function***

At *Screening Visit (V0)*: Cognitive status will be determined using the WASI-II or a comparable measure in their medical/clinical records. An IQ > 70 is required to enroll in the study. Adult participants will undergo an additional cognitive assessment, the UBACC. Participants must score within the normal range; participants who cannot pass the UBACC will not be eligible for enrollment.

For *Baseline (V1)*, *Mid-Intervention (V3)* and *Post-Intervention (V4)* Visits: We will assess cognition directly by administering the Behavior Rating Inventory of Executive Function, Second Edition (BRIEF-2), Mind Bender, and PsyToolkit's Eriksen Flanker and Wisconsin Card Sorting Tasks.

### ***ASD-related Behaviors***

We will assess ASD-related behaviors by administering the Repetitive Behavior Scale - Revised (RBS-R); Social Responsiveness Scale, Second Edition (SRS-2); Achenbach System of Empirically Based Assessment (ASEBA) - Age Dependent: Child Behavior Checklist (CBCL - parent report), Youth Self Report Form (YSR), Adult Self-Report (ASR), or Adult Behavior Checklist (ABC)

### ***Social Cognition***

We will assess social cognition and skills by administering the Dynamic Affect Recognition Evaluation (DARE), the Social Skills Improvement System - Rating Scales (SSIS-RS), and the Test of Adolescent Social Skills Knowledge (TASSK).

### ***Sensory Processing***

We will assess sensory processing by administering the SCAN-3:A Tests for Auditory Processing Disorders in Adolescents and Adults and the Brain-Body Center Sensory Scales (BBCSS).

### ***Quality of Life***

We will assess quality of life by administering the Pediatric Quality of Life Inventory (PedsQL).

### ***Intervention Embedded Assessments***

All participants, regardless of treatment group, will complete the ten sensory processing assessments before and after the first intervention period.

**The primary outcome** measures, including digital assessment completion rate, NB-SCT program adherence, usability ratings, reported adverse effects, and overall program completion rate will be used to assess feasibility, acceptability and usability of CICADAS app.

**Secondary outcomes** measures include baseline, mid-intervention, and post-intervention assessments as well as the weekly number of initiated or reciprocated social gatherings related to or in addition to PEERS assigned social activities.

### Description of Protocol Devices (Software Program)

This study employs three digital-device delivered interventions: CICADAS app, Active Control app, and PEERS. Participants assigned to receive CICADAS only will be engaged in NB-SCT exercises for a total of 40 hours during the 16-week period. Participants who are assigned to receive PEERS only will be engaged in weekly 1-hour PEERS group sessions led by a PEERS clinician during the 16-week period. Participants who are assigned PEERS + CICADAS will be engaged with the exercises for a total of 40 hours and weekly 1-hour PEERS group sessions during the 16-week period. Participants who are assigned PEERS + Active Control will be engaged with the Active Control app for a total of 40 hours and weekly 1-hour PEERS group sessions during the 16-week period.

Several elements of flexibility are allowed in the schedule to accommodate the challenges that adolescents with ASD may face:

- *Location of Use:* Some participants may experience barriers to receiving treatment, including geographic location, long waiting lists, and the requirement to take time off from school for clinic visits. This intervention is available either remote and/or in-person. Every effort will be made to schedule the weekly group sessions at a time that is most convenient for the participants. The assessments and exercises are digitally-accessible, allowing participants to complete them at different locations, as convenient.
- *Variable Number of Total Sessions:* Given fatigue (common in this population), commitments to non-study activities, health issues and/or reintegration into school, work and home life, we expect that some participants will not be able to complete the weekly PEERS sessions for 16 weeks. To accommodate this, we will be understanding of their circumstances, recommend that participants complete as many sessions as their schedule permits, and explain that the results of the trial may benefit from frequent and consistent involvement in group sessions. The site study coordinator may offer their support to work with the participant on a training schedule that is feasible, given participant's current life circumstances, as appropriate. To ensure a time-bounded study commitment, after 16 weeks such participants will perform their mid-intervention assessment (V3) or post-intervention assessment (*End of Study*, V4) visits, given that they have met the minimum number of sessions required to complete this visit.

- *Extra Time:* Under special circumstances, PEERS session(s) may be paused for 1 or more weeks. This may occur if the PEERS Clinician is unable to conduct the session and no alternate PEERS Clinician is available to conduct the session. In such cases, the intervention will be extended by the number of weeks it has been placed on hold. Participants will resume the PEERS sessions such that all 16 sessions intended for the intervention are delivered to participants.
- *Cessation of Program Use While Continuing Participation in the Study:* In some cases, a participant may wish to stop or minimize use of the program, while remaining in the study. Potential reasons for this decision might include changes in school or work circumstances, changes in residence, health issues, family/personal issues, or a lack of interest in program activities. While the participant will be encouraged to meet their weekly goals, in such cases, after discussion with the site study coordinator, the participant will be permitted to cease using the program and undergo the mid-intervention assessment (V3) or post-intervention assessment (*End of Study*, V4) visit, given they have met the minimum number of sessions required to complete this assessment.
- *Emergency:* All participants will be told how to contact the appropriate site study personnel in the case of an emergency.

Several of these options in aggregate are likely to lead to variation within a group and between groups with regard to the total number of sessions completed, and may cause an imbalance between the number of sessions completed within and between groups. Although this is not ideal, we believe that this is the correct approach given that such flexibility will allow more participants to join the study (compared to no program use flexibility), and reduce attrition. In addition, this approach has the value of more closely mimicking real-world use of the program, increasing the prospective validity of the study. We will continuously monitor the distribution of completed sessions and will consider modifications to the protocol (see *Modifications to the Protocol*) if it appears that this flexibility may be associated with meaningful differences. The data analysis plan is generally robust to variations in the number of sessions completed (see *Data Analysis*).

Each study participant will be remotely supervised by a site study coordinator. Participants may be contacted once per week by a member of the study team to discuss participant engagement with the CICADAS or Active Control apps or intervention activities, and contact may adjusted depending on each participant's needs. Based on our previous experiences with in-residence trials, we have developed protocols and training that will allow the site study coordinator and PEERS clinicians to establish rapport with participants, identify and tend to any barriers to program use or compliance (such as establishing reminders to complete assessments or reducing distracters in the environment), and to provide feedback and support

around performance. The site study coordinator and PEERS clinician will also be specifically trained to deal with specific issues that might arise with individuals with ASD.

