## General Study Design

We will employ a three-arm, active-controlled, randomized crossover trial to assess the safety and efficacy of CICADAS app in adolescents with ASD, and to evaluate its potential as a stand-alone treatment, as a primer for PEERS, or as a treatment enhancer of PEERS. We will randomize adolescents with ASD (ages 11-18) to CICADAS only, PEERS + CICADAS app, or PEERS + Active Control app.

Approximately 56 participants will be consented to ensure the successful completion of 48 participants (16 participants per treatment arm). A diagnostic interview will be performed to determine eligibility. Following inclusion and enrollment, participants will complete a set of assessments prior to the intervention to establish their baseline performance. Participants will then be randomized to the CICADAS only group (Arm A), PEERS + CICADAS app group (Arm B), or PEERS + Active Control app group (Arm C) and spend up to 16 weeks engaged in their assigned intervention. After 16 weeks, a full battery of assessments will be administered. For the next 16 weeks, Arm A will continue with PEERS only and Arms B and C will receive no treatment during this period. At the end of the intervention period, a full battery of assessments will be administered a second time to evaluate changes in performance. Finally, participants will be asked to fill out an online exit survey to rate enjoyment, usability, perceived benefits, and ease of fit into schedule.

During the first intervention period, participants assigned to the CICADAS only will complete NB-SCT exercises for 16 weeks. Participants assigned to PEERS + CICADAS will engage with the CICADAS app and complete weekly 1-hour PEERS group sessions for 16 weeks. Participants assigned to receive the PEERS + Active Control will engage in the Active Control app and complete weekly 1-hour PEERS group sessions for 16 weeks. During the second intervention period, participants assigned to receive PEERS only will complete weekly 1-hour PEERS group sessions for 16 weeks. During both intervention periods, these participants may have weekly electronic check-ins with site study personnel (as needed). The CICADAS app and the Active Control app icons, design and user experience will look the same as to not unblind the participants.

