| Emotional Face  | Emotional Conflict Resolution        | Gaze Match            | Gaze matching task           |
|   |                                      | To-do List Training   | Verbal working memory task   |
|   |                                      | In the Know           | Auditory social memory task  |
|   |                                      | Auditory Ace          | Auditory working memory task |
| *using emotionally expressive faces and emotional valence words |                                      |                       |                              |

**Active Control app:** Participants will play previously-vetted and popular casual video games for an overall duration that is time-matched to the CICADAS program. These games are designed to *not* actively engage the neural systems that underlie ASD. With this kind of control, the current study will be able to assess convergent validity (i.e., that exercises that should improve cognitive function, in fact do) and discriminant validity (that exercises that should not improve cognitive function, in fact don't). We will use control games that are designed to be a face-valid approach to cognitive training, that can be described to participants as a valid approach for improving brain health, and that support a matching of the

expectation-based influence on performance in neuropsychological outcome measures. Participants will also complete the sensory processing assessments before and after the first intervention period.

We will carefully match the CICADAS program and the active control program in overall program use intensity, modality (visual), mode of delivery (supervisor portal), time-spent attending, delivery of rewards, and overall engagement; and provide a comparison group that matches the CICADAS group on the aforementioned attributes, but without the key elements specific to improving the neuro-modulatory control of the brain. Variety and novelty are critical to maintaining participant engagement in the active control group. Here are some examples of the games below:

- Lineup Four: Line up four chips in a row before your opponent.
- Bricks Squasher II: Move a paddle and bounce the ball to destroy the bricks.
- Gems Swap: Form a line of 3 or more identical gems by swapping their positions.

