#### *Application Security*

**CICADAS and Active Control apps:** All usage and progress data collected through the CICADAS and Active Control applications are encrypted then transmitted to a central server. Data is encrypted in transit and at rest, and access is limited and audited. Data collected through the platform will not include geographic information. IP address data is stored only in memory and in request logs, and is used for technical support and troubleshooting, but not persisted with the participant's data. However, data as it relates to dates that assessments are completed is collected and stored. On the server, the data are available for review by the unblinded members including, site study coordinator, Posit Science study team, and/or other

study personnel, through a secure web portal. The study team in particular will use the secure web portal to regularly check on usage and progress of each active participant to customize their weekly phone/in-person to provide helpful guidance and coaching.

**Zoom:** This platform allows participants to communicate with others via the app without having to share their full name, mobile phone number or email to do so. Participants will choose whether to use their first name or an alias. In order to access the Zoom meeting, participants will be required to enter a passcode for their specific meeting. Once the participants enter the meeting, they will be operating within the Zoom HIPAA-compliant digital environment, and data that are produced, transmitted, and shared among users will be exclusively visible/readable to other participants and study staff. These data will include personally identifiable information—such as faces, first names or aliases, biographical and medical information—similar to what happens during all in-person group therapy sessions. Participants will be aware that the research team will have access to the group chat history and will be monitoring its contents throughout the intervention periods. As such, participants are informed that any personally identifying information voluntarily shared on this platform will be viewed by study staff. More information about how Zoom protects privacy can be found here:

<https://zoom.us/en-us/trust/privacy.html>

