## Blinding

Un-blinded Roles: PEERS clinicians and the site study coordinator are un-blinded in order to lead group sessions and support for participants using their assigned programs. They will be distinct from staff administering and scoring assessments. Additionally, designated personnel that are un-blinded may not participate in the assessment and evaluation at Mid-Intervention (V3) or Post-Intervention (V4) assessment visits of study participants.

Blinded Roles: All site staff responsible for the administration and scoring of participant assessments visits conducted after randomization will remain blinded to participant treatment. The Site Principal Investigator will be required to complete a Delegation of Authority Form, indicating which activities individual research team members will be authorized to complete. Principal Investigators will also remain blinded.

Depending upon the extent to which they are responsible for data collection and/or entry, *site study coordinators* may or may not remain un-blinded to participant treatment. This will be clarified on a site-by-site basis and will be noted on the Site Principal Investigator Delegation of Authority Form.

To prevent un-blinding, the following will occur:

1. The treatment arms will be identified as “Arm A, Arm B, and Arm C.”

2. Participants will be reminded not to discuss details related to treatment with blinded psychometricians and/or clinical evaluators during the informed consent process as well as prior to initiation, and at the conclusion of, each assessment visit;
3. Site study personnel will be instructed to not discuss details of either treatment arm during open participant groups or forums outside of the assigned group sessions or cohort discussions;
4. Site study personnel will be required execute the protocol in a manner that minimizes the possibility of accidental un-blinding of psychometricians or clinical evaluators (e.g. unintended viewing of treatment sessions);

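### Engagement contact in stage 1 is discretionary, guided by app-use data and given by staff described as un-blinded; its amount is neither equalised between the two apps nor recorded

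*Protocol*

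**What the plan says.** **Amount of contact.** The supervision paragraph of Description of Protocol Devices says "Participants may be contacted once per week by a member of the study team to discuss participant engagement with the CICADAS or Active Control apps" and lets contact vary with the participant's needs. It mentions protocols and training for this support but not their content. General Study Design likewise makes weekly electronic check-ins optional, although it is not clear which participants that sentence covers.

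**What guides it, and who gives it.** Under Application Security, "the data are available for review by the unblinded members including, site study coordinator, Posit Science study team, and/or other" study personnel, and the study team uses the portal to "regularly check on usage and progress of each active participant to customize their weekly phone/in-person to provide helpful guidance and coaching". Under Blinding, "PEERS clinicians and the site study coordinator are un-blinded in order to lead group sessions and support for participants using their assigned programs". Later in that section, site coordinators' blinding depends on their data duties and is settled site by site.

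**What is matched.** Treatment Interventions (Active Control app) says the two programs will be matched on use intensity and modality, and on "mode of delivery (supervisor portal), time-spent attending, delivery of rewards, and overall engagement". Contact with staff is not listed.

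**What depends on it.** SAP, Primary Outcome - Feasibility, analyses NB-SCT adherence in the ITT-CU population and expects at least 70% to complete 20 hours. SAP, Statistical Plan, plans an exploratory comparison of B with C over the first 16 weeks, and says the data will be used to power Phase II.

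**The concern.** Coaching can act on hours of app use and on the attention a participant receives. The sponsor's own account supports this: Sample Size Justification puts pilot attrition above 30% partly down to coordinators who lacked training in keeping participants engaged.

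Arms B and C both receive PEERS, so their comparison is the one meant to isolate the app. If staff who know the assignment give more or better coaching with one app, the B-C difference estimates app plus extra attention. The blinded assessors protect the ratings; they do not protect hours used or attention received. Without a record of contact, nobody could tell afterwards whether this had happened.

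For adherence the issue is different. A rate is reported for people who were coached, and the amount of coaching behind it is not known.

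**Working it through.** **1. The plan's own figures.** The plan gives none for contact. Its sample size is 56 recruited with 15% loss: 56 × 0.85 = 47.6, about 48 completers, and 48 / 3 = 16 per arm. Nothing below changes this.

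**2. Range of contact that complies.** There is no minimum. Reading once a week as a ceiling, a participant may receive 0 to 16 contacts over 16 weeks. If the adjustment can go upward, the number could be higher.

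**3. What is equal and what is recorded, B versus C.**

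| Item | Equal between apps? | Recorded? |
|---|---|---|
| App time and engagement | Stated as matched | Usage held on the portal |
| Payment for app use | Same rule, up to $10 a week | Paid weekly |
| App appearance | Stated to be the same | Not applicable |
| Staff contact | Same optional wording; no schedule, script or equality rule | No count or minutes required |

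The nearest records are emails judged significant (Data Management), forms for symptom deterioration (Reporting of Serious Adverse Effects) and monitoring of completed sessions (Description of Protocol Devices). None of these measures contact. The assessment table in Appendix I has no contact item, and the SAP's mixed model has no contact term.

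**4. Possible size in the B-C comparison.** The documents give no coaching effect, so the bias values are assumptions, in SD units of the analysed change. Two-sided alpha of 0.05 is also assumed, because the SAP gives 0.05 without sidedness. Normal approximation:

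- SE of the difference = √(2/16) = 0.354 SD.
- Effect detectable with 80% power = (1.960 + 0.842) × 0.354 = 0.99 SD.
- With no true effect and bias b, rejection probability = Φ(b/SE − 1.96) + Φ(−b/SE − 1.96).

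| Assumed bias b (SD) | Rejection rate |
|---|---|
| 0 | 5% |
| 0.1 | 5.9% |
| 0.2 | 8.7% |
| 0.3 | 13.6% |
| 0.5 | 29.3% |

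With an assumed true effect of 0.5 SD, power is 29%. A bias of 0.3 SD toward control lowers it to 8%; the same bias toward CICADAS raises it to 62%.

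For Phase II, the required number per arm varies with 1/d². An estimate of 0.8 in place of 0.5 gives (0.5/0.8)² = 0.39 of the needed size; an estimate of 0.2 gives (0.5/0.2)² = 6.25 times that size. For proportion, a bias of 0.3 SD is 0.3/0.354 = 0.85 of one standard error, so random error is at least as large.

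**5. Adherence.** If ITT-CU is Arm B with 16 people, reaching 70% needs 12 of 16 (0.7 × 16 = 11.2). If Arm A also counts, it needs 23 of 32 (0.7 × 32 = 22.4). Binomial probability of reaching it:

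| True rate under the coaching given | n = 16 | n = 32 |
|---|---|---|
| 60% | 0.167 | 0.116 |
| 70% | 0.450 | 0.495 |
| 75% | 0.630 | 0.737 |

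If coaching moved the rate from 60% to 75% (an assumption), the chance of meeting the expectation would rise from 17% to 63% with 16 people. This shows how far the result could depend on the support given. It does not show a bias.

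**The case against.** The strongest case against is that one sentence covers both apps with the same weekly wording, every participant is to be supervised, and protocols and training are said to exist. Those materials are not in the documents, so a script may exist. Payment and appearance are the same, completed sessions are monitored, and assessors after randomization are blinded. Efficacy is secondary, and the SAP says it is underpowered. All of this stands and limits the point. It does not make contact equal: the wording permits contact with both apps without requiring the same amount, the stated purpose of the training is rapport, barriers and feedback, and session monitoring sees the result of coaching rather than its dose.

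Three stronger readings are tempting, and the documents do not support them:

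- *The protocol promises equal supervision and then breaks the promise.* The matching list names a supervisor portal, which is a route of delivery. It does not name supervision.
- *Coaching biases the primary adherence outcome.* That outcome is a one-group description of NB-SCT use, and Arm C has no NB-SCT. The Overview calls CICADAS clinician-assisted, so support may be part of the product.
- *Un-blinded staff will favour CICADAS.* Nothing shows that contact will differ by arm. The sponsor staff's disclosed financial interest is a reason for a written rule, not evidence of unequal treatment. The coordinator's blinding is itself stated in two ways.

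**Conclusion.** The point holds as a cheap improvement. Contact is discretionary and usage-informed, the portal users who tailor it are described as un-blinded, and nothing in the documents equalises it between apps or records its amount. The B-C comparison is therefore open to a bias of unknown size and either direction. At an assumed 0.1 to 0.3 SD, the false-positive rate would be 5.9% to 13.6% instead of 5%, and the Phase II planning estimate would shift by the full bias. These sizes rest on 16 per arm, a normal approximation, a two-sided test and assumed coaching effects.

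For adherence, the conclusion is only that the rate describes coached use with an unstated amount of coaching. A reader might infer that Phase II could not reproduce it. That goes too far: the support behind the rate would be undocumented, which makes comparison harder but not impossible. The main feasibility aim is not undermined.

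**What to change.** Amend the supervision paragraph of Description of Protocol Devices, and Application Security, so that engagement contact in stage 1 follows the same offered schedule and the same script for both apps, whatever the assignment. Log the number, minutes and reason of each contact. In the SAP, report these by arm beside adherence, and state that the 70% expectation refers to coached use. Reconcile the two statements in Blinding on the site coordinator.

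Keep PEERS contact and safety or symptom contact outside any limit, but log them. Staff are to ask about deterioration at each contact, so the schedule must not restrict those enquiries. An offered schedule is preferable to contact triggered by low use, because such a trigger would send more coaching to whichever app is less engaging.

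The cost is a short contact procedure, one log form and slightly less freedom to tailor support. The sample size does not change.
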